10.6 Appendix 6: Criteria for Identifying Vital Signs of Potential Clinical Relevance

Variable	Criterion Value ^a	Change Relative to Baseline ^a
Heart rate ^b	> 100 bpm < 50 bpm	≥ 10 bpm increase ≥ 10 bpm decrease
Systolic blood pressure ^b	≥ 140 mmHg Supine < 90 mmHg	≥ 20 mmHg increase ≥ 20 mmHg decrease
Diastolic blood pressure ^b	≥ 90 mmHg Supine < 60 mmHg	≥ 10 mmHg increase ≥ 10 mmHg decrease
Orthostatic hypotension	≥ 30 mmHg decrease in systolic blood pressure and/or a decrease of ≥ 20 mmHg in diastolic blood pressure after at least 3 minutes of standing compared to the previous supine blood pressure.	Not applicable (baseline status not considered)
Orthostatic tachycardia	≥ 25 bpm increase in heart rate from supine to standing	Not applicable (baseline status not considered)
Weight	—	≥ 7% increase ≥ 7% decrease

bpm = beats per minute.

^aIn order to be identified as potentially clinically relevant, an on-treatment value must meet the “Criterion Value” and also represent a change from the subject’s baseline value of at least the magnitude shown in the “Change Relative to Baseline” column.

^bAs defined in “Supplementary Suggestions for Preparing an Integrated Summary of Safety Information in an Original New Drug Application Submission and for Organizing Information in Periodic Safety Updates,” FDA Division of Neuropharmacological Drug Products draft (2/27/87).

10.7 Appendix 7: Criteria for Identifying ECG Measurements of Potential Clinical Relevance

Variable	Criterion Value ^a	Change Relative to Baseline ^a
Rate		
Tachycardia	≥ 120 bpm	increase of ≥ 15 bpm
Bradycardia	≤ 50 bpm	decrease of ≥ 15 bpm
Rhythm		
Sinus tachycardia ^b	≥ 120 bpm	increase of ≥ 15 bpm
Sinus bradycardia ^c	≤ 50 bpm	decrease of ≥ 15 bpm
Supraventricular premature beat	all	not present → present
Ventricular premature beat	all	not present → present
Supraventricular tachycardia	all	not present → present
Ventricular tachycardia	all	not present → present
Atrial fibrillation	all	not present → present
Atrial flutter	all	not present → present
Conduction		
1 atrioventricular block	PR ≥ 200 msec	increase of ≥ 50 msec
2 atrioventricular block	all	not present → present
3 atrioventricular block	all	not present → present
Left bundle-branch block	all	not present → present
Right bundle-branch block	all	not present → present
Pre-excitation syndrome	all	not present → present
Other intraventricular conduction block ^d	QRS ≥ 120 msec	increase of ≥ 20 msec
Infarction		
Acute or subacute	all	not present → present
Old	all	not present → present
		≥ 12 weeks post trial entry
ST/T Morphological		
Myocardial ischemia	all	not present → present
Symmetrical T-wave inversion	all	not present → present
Increase in QTc	QTcF > 450 msec (males) QTcF > 470 msec (females)	

QTc = corrected QT interval; QTcF = QT interval corrected for heart rate using Fridericia's formula.

^aIn order to be identified as potentially clinically relevant, an on-treatment value must meet the "Criterion Value" and also represent a change from the subject's baseline value of at least the magnitude shown in the "Change Relative to Baseline" column.

^bNo current diagnosis of supraventricular tachycardia, ventricular tachycardia, atrial fibrillation, atrial flutter, or other rhythm abnormality.

^cNo current diagnosis of atrial fibrillation, atrial flutter, or other rhythm abnormality.

^dNo current diagnosis of left bundle branch or right bundle branch block.

10.8 Appendix 8: Protocol Amendments

The investigator will not make any changes to this protocol without the sponsor's prior written consent and subsequent approval/favorable opinion by the IRB/IEC. Any permanent change to the protocol, whether an overall change or a change for specific trial site(s), must be handled as a protocol amendment. Any amendment will be written by the sponsor. Each amendment will be submitted to the IRB/IEC, as required by local regulations. Except for "administrative" or "nonsubstantial" amendments, investigators will wait for IRB/IEC approval/favorable opinion of the amended protocol before implementing the change(s). Administrative amendments are defined as having no effect on the safety of subjects, conduct or management of the trial, trial design, or the quality or safety of IMP(s) used in the trial. A protocol change intended to eliminate an apparent immediate hazard to subjects should be implemented immediately after agreement by the sponsor and investigator, followed by IRB/IEC notification within local applicable timelines. The sponsor will submit protocol amendments to the applicable regulatory agencies within local applicable timelines.

When the IRB/IEC, investigators, and/or the sponsor conclude that the protocol amendment substantially alters the trial design and/or increases the potential risk to the subject, the currently approved written ICF will require similar modification. In such cases, after approval/favorable opinion of the new ICF by the IRB/IEC, repeat written informed consent will be obtained from subjects enrolled in the trial before expecting continued participation and before the amendment-specified changes in the trial are implemented.

10.8.1 Protocol Amendment(s)/Administrative Change(s)

10.8.1.1 Protocol Amendment 1

Amendment 1 Approval Date: 01 Jul 2020

PURPOSE:

The purpose of this protocol amendment is to introduce an addendum for COVID-19 for any protocol-specified activities that are not able to be performed or cannot be performed due to COVID-19 considerations. Refer to the COVID-19 Addendum (dated 01 Jul 2020) for the appropriate measures to be followed. Additional administrative changes were made to the protocol and are documented below. Finally, minor editorial revisions were made for consistency with Otsuka style and for internal consistency.

BACKGROUND:

These changes to clinical trial protocol 331-201-00195, originally issued on 21 Aug 2019, were made to introduce a COVID-19 addendum. In addition, administrative changes were incorporated as described in the protocol clarification memos (dated 20 Nov 2019 and 12 Feb 2020).

MODIFICATIONS TO PROTOCOL:

General Revisions:

- Clarified in the trial design sections, for consistency with the schedule of assessments, that an optional telephone call or other form of communication will be made with the subject approximately 1 week (\pm 2 days) after the visit (eg, at Weeks 3, 5, 7, 9, and 11) to check on status.
- Modified exclusion criterion #1 to indicate that consensual sexual activity that cannot biologically result in pregnancy may not be subject to required birth control methods (following discussion with the medical monitor).
- Added to exclusion criterion #6 that if the major protocol deviation is due to COVID-19, eligibility for the subject to continue can be discussed with medical monitor.
- Added that rescreening of subjects is not permitted.
- For medications prohibited during the trial, added an exception for gabapentin when used to treat anxiety or pain (after discussion with the medical monitor).
- Added trazodone to the list of medications prohibited during the trial (unless it is being used for sleep management, in which case further discussion with the medical monitor is required).

- CCI
- Added that the investigator (or their designee participating in the trial) will record information to document all significant observations at remote visits (in addition to site visits).
- Incorporated the following items from the protocol clarification memos:

Table 3.2-1 Dosing Schedule**Error! Bookmark not defined.**

List of In-text Figures

Figure 3.1-1	Trial Design Schematic	8
--------------	------------------------------	---

1 Introduction

This statistical analysis plan (SAP) documents the statistical methodology and data analysis algorithms and conventions to be applied for statistical analysis and reporting of efficacy and safety data of study 331-201-00195. All amendments and addendums to the protocol are taken into consideration in developing this SAP. In addition, if the analyses described in the protocols differ from those in this SAP, the methods of the SAP prevail.

2 Study Objectives

Primary Safety: To evaluate the safety and tolerability of brexpiprazole for the treatment of subjects with a diagnosis of BPD.

3 Trial Details

3.1 Study Design

This is a 12-week, multicenter, open-label trial designed to evaluate the safety and tolerability of brexpiprazole treatment in adult subjects diagnosed with BPD. Subjects will receive 2 to 3 mg/day brexpiprazole.

Enrollment into the trial will be drawn from eligible subjects who completed the last treatment visit of the previous double-blind brexpiprazole BPD trials (and took the investigational medicinal product [IMP] through the last scheduled treatment visit) and, in the investigator's judgment, could potentially benefit from treatment with brexpiprazole for BPD.

The trial will be organized as follows:

[figure not shown]
Screening/Baseline: Subjects will be screened for eligibility at the last scheduled treatment visit of the previous double-blind trial. Subjects will sign a separate informed consent form (ICF) at the last scheduled treatment visit of the previous double-blind trial for participation in this trial before any procedures specific to the open-label trial are performed. The assessments from the last scheduled treatment visit of the previous double-blind trial will serve as the baseline measures for this trial for any assessment that is not new (unique) to the open-label trial. Medical history will be updated, if necessary. Informed consent cannot be obtained after the last scheduled treatment visit of the previous double-blind trial without all screening/baseline assessments being repeated. If a subject is unable to rollover immediately, up to 3 days may be permitted between the end of the double-blind trial and the start of IMP in the open-label extension trial; however, this must be discussed with the medical monitor (Note: assessments from the last scheduled treatment visit in the previous double-blind trial that are going to be used as the baseline measures for Trial 331-201-00195 will not need to be repeated if the subject enters Trial 331-201-00195 within 3 days).

Due to COVID-19, delayed entry subjects are permitted to be screened for Trial 331-201-00195 up to 90 days after completing the last scheduled treatment visit of the previous double-blind BPD trial (discussion with the medical monitor is required if > 90 days have passed). These subjects will be screened for eligibility at a separate screening visit for Trial 331-201-00195, where they will undergo full assessments to determine eligibility. The screening period will be up to 21 days and may be extended upon discussion with the medical monitor. The delayed entry subjects will also undergo a separate baseline visit, and the assessments from that visit will serve as the baseline measures for Trial 331-201-00195. Delayed entry subjects will receive the first dose of IMP at the baseline visit.

Treatment Phase: Eligible subjects will receive daily treatment with open-label brexpiprazole beginning at the screening/baseline visit. Visits will occur at the end of Weeks 2, 4, 8, and 12. Telephone contact will be made at Weeks 1, 6, and 10 to assess adverse events (AEs) and concomitant therapy. In addition, an optional telephone call or other form of communication will be made with the subject approximately 1 week (\pm 2 days) after the visit (e.g., at Weeks 3, 5, 7, 9, and 11) to check on status. All subjects will receive up to 12 weeks of open-label treatment in this trial.

Follow-up: Subjects will be followed for safety via telephone contact or clinic visit 21 (\pm 3) days after the last dose of open-label brexpiprazole.

See [Figure 3.1-1](#) for a schematic of the trial design.

^aThe last visit of the previous double-blind BPD trial will serve as the baseline measures for Trial 331-201-00195. If a subject is unable to rollover immediately, up to 3 days may be permitted between the end of the double-blind trial and the start of IMP in the open-label extension trial; however, this must be discussed with the medical monitor.

^bTelephone contact or clinic visit.

^cTelephone contact will be made at Weeks 1, 6, and 10 to assess AEs and concomitant therapy.

Figure 3.1-1 Trial Design Schematic

3.2 Trial Treatments

The first dose of open-label brexpiprazole will be taken one day after the last dose of double-blind IMP is taken for the previous double-blind, brexpiprazole BPD trial so that treatment continues without interruption. It is anticipated that the last dose of IMP of the double-blind trial will be taken the day of the treatment last visit of the previous double-blind brexpiprazole BPD trial (i.e., the day of the screening/baseline visit for the open-label trial). If a subject is unable to rollover immediately, up to 3 days may be permitted between the end of the double-blind trial and the start of IMP in the open-label extension trial; however, this must be discussed with the medical monitor. Delayed entry subjects will receive the first dose of IMP at the baseline visit. All subjects will receive a starting dose of 1 mg/day at the screening/baseline visit, followed by an increase to 2 mg/day at the end of Week 1 (Table 3.2-1). Subjects may increase their dose to 3 mg/day at the investigator's discretion on or after the Week 2 visit, depending on treatment response and tolerability. Subjects taking 3 mg/day may down-titrate to 2 mg/day based on tolerability at any time during the course of the trial. Subjects unable to tolerate 2 mg/day will be discontinued from the trial. Dose adjustments to brexpiprazole must be made in increments of 1 mg/day. Dose decreases for brexpiprazole can occur at unscheduled visits and dose increases for brexpiprazole can only occur at scheduled visits.

As applicable, dose changes of background antidepressant therapy (ADT) can be modified to achieve optimum efficacy and tolerability. Dose adjustments of ADT should not occur at the same visit as a dose adjustment of brexpiprazole and a recommended minimum of 5 days should occur between any dose adjustments of brexpiprazole or ADT at any point during the trial.

Table 3.2-1 Dosing Schedule			
IMP	Screening/Baseline - Week 1	Week 1 - Week 2	Week 2 - Week 12 ^a
Brexipiprazole	1 mg/day	2 mg/day	2 or 3 mg/day ^b

^aDown titration can occur at any time due to tolerability after Week 2. The minimum dose allowed is 2 mg/day.

^bOption to titrate to 2 or 3 mg/day (i.e., 2 mg, or 3 mg) based on clinical response and tolerability; changes must occur in 1 mg/day increments.

4 Sample Size and Power Justification

The sample size is not based on statistical power considerations but on the number of subjects rolling over from the lead-in trials. The trial population will be derived from eligible subjects

who completed the previous double-blind brexpiprazole BPD trials. The number of eligible subjects will be limited by the number of subjects enrolled into the double-blind trials.

5 Data Sets for Analysis and Missing Data

5.1 Data Sets for Analysis

The following datasets are defined for this trial:

- Enrolled Sample, which comprises all subjects who sign an ICF for the trial and are enrolled into the trial.
- Safety Sample, which comprises all subjects who will receive at least 1 dose of IMP.
- CCI

5.2 Handling of Missing Data

In order to assess the sensitivity of results due to missing data, 2 types of analyses will be performed: last observation carried forward (LOCF) and observed cases (OC). The OC dataset will consist of the actual observations recorded at each visit. The LOCF dataset will include data recorded at a scheduled visit, i.e., all OC data, or, if no observation is recorded at that visit, data will be carried forward from the previously scheduled visit. Baseline data will not be carried forward to impute missing values for the LOCF dataset. The OC dataset will be used for analyses at each trial visit and the LOCF dataset will be used for analyses at the last visit.

6 Study Conduct

6.1 Subject Disposition, Completion Rate and Reasons for Discontinuation

Subject disposition will be summarized for the Enrolled Sample by parent study treatment group and overall.

Subject completion rate and reasons for discontinuation will be summarized for the Enrolled Sample by parent study treatment group and overall.

6.2 Treatment Compliance

Based on the Investigational medicinal product (IMP) panel of the CRF, compliance in taking IMP is calculated by dividing the number of tablets/capsules taken by the total number of

tablets/capsules the patients were scheduled to take during the study period. For lost-to-follow up patients, last IMP end date record will be used as the treatment end date.

6.3 Protocol Deviation

Protocol deviations will be summarized by center and type of deviation for enrolled subjects by parent study treatment group. A listing of protocol deviations will be provided. In addition, protocol deviations affected by the COVID-19 will be summarized. Listing of subjects with protocol deviations affected by the COVID-19 will also be provided.

7 Baseline Characteristics

7.1 Baseline Definition

Baseline is defined as the last available measurement prior to the first dose of open-label IMP in the open-label treatment phase.

7.2 Demographic Characteristics

Baseline demographic characteristics including age, race, ethnicity, gender, weight, height, and body mass index (BMI) will be summarized by descriptive statistics (frequency, mean, median, standard deviation, maximum, minimum, and percentage when applicable) for the Enrolled Sample by parent study treatment group and overall.

7.3 Medical and Psychiatric History

A summary of medical, psychiatric, and borderline personality disorder history will be presented for the Enrolled Sample (by parent study treatment group and overall).

7.4 Baseline Psychiatric Evaluation

For the Enrolled Sample, baseline psychiatric scale evaluation will be summarized by parent study treatment group and overall. The mean, median, range and standard deviation will be used to summarize the assessments of: CCI [REDACTED]

8 Efficacy Analysis

CCI [REDACTED]

CCI

CCI

8.1 COVID-19 Related Supplementary Analyses

Summary statistics for mean and mean change from baseline in CCI [REDACTED], by trial visit and at the last visit (i.e., Week 12/ET) and by visit type (face-to-face vs. remote) based on the Efficacy Sample will be provided by parent study treatment group for rollover subjects and overall.

9 Safety Analysis

The primary safety endpoint analysis is the frequency and severity of AEs in the open-label treatment phase (see [Section 9.1](#)). Other standard safety variables to be analyzed include clinical laboratory tests, vital signs, body weight, waist circumference, BMI, 12-lead electrocardiograms (ECGs), and physical examinations. In addition, data from the following safety scales will be evaluated: Abnormal Involuntary Movement Scale (AIMS), Simpson-Angus Scale (SAS), Barnes Akathisia Rating Scale (BARS) and Columbia-Suicide Severity Rating Scale (C-SSRS).

Safety analyses will be conducted based on the Safety Sample, and summary statistics will be provided by parent study treatment group and overall, unless otherwise indicated.

Unless otherwise specified, in general, analysis of safety data will be performed on observed case and for last visit.

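### SAP 9 does not separate rollover from COVID-19 delayed-entry subjects, so baseline-dependent safety results in the prior-brexpiprazole column mix on-drug baselines with baselines taken after a break

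*SAP*

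**What the plan says.** **Who is analysed and in which columns.** SAP 5.1 defines the "Safety Sample, which comprises all subjects who will receive at least 1 dose of IMP". SAP 9 Safety Analysis reports that sample as follows: "summary statistics will be provided by parent study treatment group and overall, unless otherwise indicated". SAP 9.1 (AEs), 9.2 (laboratory) and 9.2.2 (metabolic) repeat treatment-group columns without mentioning entry type.

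**Rollover subjects.** Under SAP 3.1 their baseline is the last scheduled double-blind visit. SAP 3.2 expects the last double-blind dose to be taken that same day. If immediate rollover is not possible, "up to 3 days may be permitted between the end of the double-blind trial and the start of IMP in the open-label extension trial".

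**Delayed-entry subjects.** SAP 3.1 adds that, because of COVID-19, "delayed entry subjects are permitted to be screened for Trial 331-201-00195 up to 90 days after completing the last scheduled treatment visit", or later after discussion with the medical monitor. It continues: "The screening period will be up to 21 days and may be extended upon discussion with the medical monitor". They then have a separate baseline visit, and "the assessments from that visit will serve as the baseline measures for Trial 331-201-00195".

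**Baseline.** SAP 7.1 gives one definition for everyone: the last value before the first open-label dose.

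**A nearby contrast.** The supplementary summaries in SAP 8.1 "will be provided by parent study treatment group for rollover subjects and overall". SAP 9 has no such qualifier.

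**The concern.** For a rollover who took brexpiprazole in the parent trial, change from baseline means change while exposure continues. For a delayed-entry subject who took it, change from baseline means change on restarting after trial drug had stopped. These are different quantities, and one column would average or count them together.

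A small mean change in that column could mean that the drug does little, or that its effect was already present at an on-drug baseline. A shift or flag could reflect late worsening on continued drug, or the return of an effect that faded during the break. As the visible tables stand, a reader could not tell these apart. No listed table title reports how many delayed-entry subjects a column contains.

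Safety is the trial's only visible objective. The affected outputs (ECG, vital signs, laboratory tests, weight, EPS scales and C-SSRS) are the secondary safety endpoints in protocol section 3.

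**Working it through.** The plan states no sample size, power or expected rate, so there is no figure to reproduce. The check is mainly textual, with simple arithmetic.

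**1. Are delayed-entry subjects in the parent-group safety columns?** They are dosed, so SAP 5.1 puts them in the Safety Sample. They completed a parent trial, so each has a parent treatment group. SAP 9 allows exceptions where indicated. SAP 9.1 to 9.8, Appendices 1 to 3 and the table list in SAP 12 visibly indicate none by entry type. Pooling is the plain reading.

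**2. How far apart are the two baselines?** Inputs are from SAP 3.1.
- Rollover: baseline is at the last double-blind visit, with at most 3 days to open-label dosing.
- Delayed entry: 90 days to screening + 21 days of screening = 111 days from the last double-blind visit. This assumes that the baseline visit comes at the end of screening. Both limits can be extended, and individual gaps may be much shorter.
- For scale, the treatment period is 12 × 7 = 84 days, and 111 / 84 = 1.32.

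**3. Which outputs depend on baseline?**
- Mean changes in laboratory values, vital signs, weight, BMI, waist, ECG, SAS, AIMS and BARS.
- SAP 9.2.1 liver criteria, which offer baseline as an alternative to ULN, and SAP 9.2.2 lipid and glucose shifts.
- Appendix 1 heart-rate, blood-pressure and weight flags; Appendix 2 hematocrit and urinalysis criteria; Appendix 3 criteria that require a change.
- SAP 9.4 QT/QTc new-onset and increase categories.
- SAP 9.6 treatment-emergent C-SSRS categories.

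In SAP 9.1, a TEAE that starts on drug does not depend on a baseline measurement. Only the part of the definition covering events already present at baseline does.

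**4. What can mixing do? (illustration on assumed values)** Suppose two subjects each gained 7% in weight on double-blind drug.
- A rollover who then stays at that weight shows 0% change here.
- A delayed-entry subject who lost all of the gain in the gap and regains it shows 1.07 / 1.00 − 1 = 7.0% and is flagged.
- One who lost half shows 1.07 / 1.035 − 1 = 3.4%.

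All three end at the same weight relative to pre-drug weight.

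**5. How far could a pooled rate move? (assumed rates)** With delayed-entry share f, pooled rate = (1 − f) × rollover rate + f × delayed-entry rate. Take 5% in rollovers and 10% to 15% in delayed-entry subjects:

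| f | Pooled rate |
|---|---|
| 5% | 5.25% to 5.5% |
| 10% | 5.5% to 6% |
| 20% | 6% to 7% |
| 30% | 6.5% to 8% |

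Neither the rates nor f are in the documents. The table shows only that the effect is slight when f is small and grows with it.

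**6. Separate point: the weight flag.** Appendix 1 flags a change of at least 7% from the open-label baseline, with no absolute criterion. A rollover gaining 5% in the parent trial and 5% here has 1.05 × 1.05 − 1 = 10.25% in total and is not flagged.

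**The case against.** **The term rollover may cover everyone.** SAP 4 bases the sample size "on the number of subjects rolling over from the lead-in trials", which describes the whole population. If SAP 8.1 uses the word that way, it does not differ from SAP 9. No visible text settles this. SAP 8 and one analysis set in SAP 5.1 are redacted, and the COVID-19 Addendum named in Protocol Amendment 1 is not among the documents. This stands: a reader might infer that SAP 8.1 and SAP 9 contradict each other, but that is not established. The pooling does not rest on the contrast; it follows from SAP 3.1, 5.1, 7.1 and 9.

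**No distortion is shown.** This also stands. The 111 days is a permitted standard maximum, not an observed gap, and ratios of permitted gaps measure no bias. A gap does not show that weight or lipids returned to pre-drug levels. What subjects took in the gap is not stated. With few delayed-entry subjects the effect would be negligible.

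**The 7-day limit in SAP 10.1 is not a washout standard.** It might be read as the SAP's own line between on-drug and off-drug values. It is a visit-mapping rule for rating scales after the last open-label dose, and does not cover weight, laboratory values or ECG.

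**The primary endpoint is largely untouched.** A reader might infer that the AE tables are compromised too. Counts of new-onset TEAEs are not defined by baseline, and protocol 9.4.2.1 plans them by prior treatment group. AE incidence may differ between continued exposure and re-exposure, but that does not justify re-cutting every AE table.

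**Restarting weight at open-label entry is the stated design.** This stands too. Protocol section 3, SAP 7.1 and the 7% rule in both documents agree. Gains of 7% or more within this trial are still flagged, and weight gain reported as an AE still counts.

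**Conclusion.** The concern holds for baseline-dependent safety outputs in the prior-brexpiprazole column. As visibly written, SAP 9 pools subjects whose baseline is on trial drug with subjects whose baseline may follow a standard gap of up to 111 days. Following the plan exactly would give change and shift results that blend continued exposure with re-exposure.

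The size is unknown, and no direction or amount of distortion is claimed. The conclusion assumes that at least some delayed-entry subjects took brexpiprazole in the parent trial, and that no redacted text or addendum already separates entry types. The documents do not list the parent-trial arms. If one was placebo, its column has no on-drug versus off-drug contrast.

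The documents do not support extending this to the AE counts as a whole, or calling the weight restart an error. This is a worthwhile, inexpensive improvement to a descriptive safety report; it does not show that the safety conclusions would be wrong.

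**What to change.** In SAP 9:

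1. Define rollover as a first open-label dose within 3 days of the end of the double-blind trial. Define delayed entry as every other dosed subject. Use the terms the same way in SAP 4 and SAP 8.1.
2. Report the number of each entry type by prior treatment.
3. For the baseline-dependent outputs listed in the check, present the parent-group columns for rollovers, show delayed-entry subjects separately by prior treatment, and keep the overall column.
4. Leave the AE tables by prior treatment group, as protocol 9.4.2.1 plans, with at most one supplementary TEAE overview by entry type.

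This needs no new data. It costs a few extra tables. Delayed-entry cells may be small and only descriptive, and the overall column still mixes baselines, so a footnote should say so.

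Optionally, for prior-brexpiprazole rollovers, add a supplementary summary of weight change and the 7% flag from the parent-trial pre-treatment baseline, keeping the open-label baseline as the main one. This needs a cross-trial derivation and parent-trial weights; the documents do not show what was recorded.
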